- 3) [name], RN, FAAN, Independent reviewer, School of Nursing Associate Dean for Research, Distinguished Professor, will perform an independent review of the expected/unexpected adverse event data to assure non-bias by the PI on a monthly basis.

Minimizing research-associated risk.

- Protocols for teaching patients how to safely apply the electrodes and monitor their skin will be verbalized with the patient. Following the teaching the patient will teach back what was learned. If not complete or correct, additional information will be given with the patient again verbalizing all key points. If the patient is unable to complete this task, they will be excluded from the study. We will provide written handouts with directions and pictures of proper placement of electrodes. The RA will call the patients weekly while they are using the EMPI machine to determine safety and potential skin irritation or muscle soreness.
- For patients who have scores on the PHQ-8 suggestive of high depressive symptoms (scores > 10) [name] will follow-up with patients' individual physicians after alerting the patient.
- Adherence to the safety protocols will be reviewed at weekly team meetings and at monthly Co-Investigator meetings. In addition, [name] will provide continuous, close monitoring of protocol adherence and referral of patients if needed.

[name] will be responsible for reporting unexpected adverse events and unanticipated problems as required by the IU IRB. The IU IRB will be notified in writing of adverse events within 5 business days of identification of events. During each visit, the PI or RA will question the patient about adverse events using an open question, taking care not to influence the patient's answers, e.g. "Have you had any unusual symptoms or medical problems since the last visit?" It is expected that many HF patients will have events that are commonplace due to their HF and associated comorbidities.

Determining if an Adverse Event needs to be reported to the IRB

1. Is the occurrence **unexpected** during the course of the study?
 - a. We expect skin irritation and minor muscle soreness, complications that occur as a result of protocol-mandated use of the EMPI machine, these events will not be reported.
2. Is the occurrence related (or possibly related) to the study?
 - a. Not including the expected events, if yes and unexpected, then the event will be reported to the IRB.
3. Does the event put participants at greater risk of harm?
 - a. Is there something we could change in the protocol to decrease the likelihood of another event, if yes, then modification will be submitted.
 - b. Was this participant specific and unlikely to happen to other participants? If yes, no changes will be made.

Each reported adverse event will be described by its duration (i.e., start and end dates), and suspected relationship to study protocol. These relationships are categorized as likely, possible, and not related. To ensure consistency, PI will apply the following general guideline:

- Yes - There is a plausible relationship between the onset of the adverse event and administration of the study protocol.
 - The adverse event cannot be readily explained by the subject's clinical state, inter-current illness, or concomitant therapies; event abates or resolves upon discontinuation of use of the EMPI machine.
 - No - Evidence exists that the adverse event has an etiology other than the study protocol (e.g., preexisting medical condition, underlying disease, inter-current illness, or concomitant medication); and/or the adverse event has no plausible relationship to the study.

The RA will notify the PI of any event if found when PI was not present and give all information collected so far. The PI will review the medical chart to assist in determining potential causes if necessary. Next, the PI will contact members of the clinical care team to clarify uncertainty related to inadequate documentation, if necessary. Third, if the PI is unable to decide for certain if an adverse event is study related, he or she will have the option of sending a personal health identifier-stripped, written narrative of the event to the other co-PIs who will assist as to whether the event constituted an adverse event. All adverse events will be followed through resolution, stabilization, or until the subject is lost-to-follow-up.

[name] will conduct a literature search and review scientific reports monthly to determine if new studies/protocols/warnings have been published about NMES/TENS interventions in HF or other conditions. If new publications are found, they will be reviewed by the PI and if deemed important, Co-Investigators for impact on the safety of participants or ethics of the study.

Section 7: Study Withdrawal/Discontinuation

A participant may withdrawal from the study at any time verbally or by providing this request in writing as described in the informed consent document. As outlined in the consent document, if the participant/patient wishes to withdraw consent, the PI will not take back any research/analyses already completed.

Section 8: Statistical considerations

Data Management and Analysis

Data collection will occur at the CTSI in IU Health main campus. All data are entered online using the REDcap system. REDcap is a secure web based application for building and managing databases, sponsored by a consortium of 118 research institutions. It offers a streamlined process for building a database, interface for data collection and validation, and automated export procedures for downloading to statistical packages. All REDcap data are stored on a secure web server located behind a firewall on the CCTS network. The ActivPal data will be downloaded from the device directly to a Box Health account with Study ID used as the identifier.

The risk of breach of confidentiality of patient data will be minimized by ensuring all involved personnel have a full understanding of the Health Insurance Portability and

Accountability Act (HIPAA) rules and the protection of privacy guidelines for conducting medical record reviews through the completion of all IRB-mandated HIPAA training and education. Data gathering instruments and procedures are carefully designed to limit the access of personal information. Password protected laptop dedicated for this study only will be used to enter data. Each participant will be assigned a unique identification number and all of their records marked only with this number. All hard copies of data (consents) will be kept in a locked file in the PI's office separate from the files containing the identification key. All digital data reside on computers with encryption software that are password protected and that are kept in locked offices in a locked office suite available only to members of the research team.

Missing Data

The research associate will review all data collected for completeness and readability, correcting any errors prior to data analysis. We will collect "reason for drop out" if a participant stops the study. We will continue to try to schedule subsequent data collection interviews even if the participant is not able to complete a previous one. During each data collection session, team members will work with participants to encourage response to all items and will review data to ensure all data points are completed unless the participant prefers not to answer. Nonetheless, missing data will occur and this will be acknowledged in the analysis.⁷⁶ We will conduct initial analyses using the maximum likelihood approach, as it emphasizes the use of all available data. The use of random effects modeling techniques, in particular repeated measures mixed modeling, allows for missing data by adjusting the estimation process to account for bias resulting from data missing at random. Baseline data from those with and without missing data will be compared to determine whether there are systematic differences, using demographic and personal variables. If the data are not amenable to the maximum likelihood method random effects analysis, multiple imputation will be used as an alternative procedure for handling missing data. Multiple imputation produces results similar to maximum likelihood when used under identical conditions. We will use multiple imputation in the sensitivity analyses; this will allow for the comparison of study results under a variety of assumptions to assess the robustness of the findings.

Statistical Analysis

Data analysis will be done using SPSS, v. 22; an alpha level of .05 will be used for all tests except where noted. Study measures will be examined using univariate statistics, including means, standard deviations and frequency distributions, and graphical techniques, such as box plots and histograms. Distributions for continuous outcome measures will also be examined for violations of normality using normal probability plots. If there is evidence of lack of normality for a particular outcome, transformations (e.g., logarithmic) will be used so that the distribution of the transformed variable more closely approximates normality. The analysis strategy to be used to test all aims is repeated measures analysis of variance (ANOVA). Each ANOVA model will include the main effects of Time (baseline, 6 weeks, 6 months' post intervention period) and Group (intervention and sham intervention), as well as the Time by Group

interaction. Post-hoc pairwise comparisons of means will be done using Fisher least significant difference procedure. The repeated measures models will be estimated using the MIXED procedure in SAS. This analysis will: **test the effect of NMES on muscle mass and strength in those with HF (Aim 1); evaluate the effect of NMES on exercise capacity and activity (Aim 2); and assess the effect of NMES on HF symptoms and quality of life (QOL); and finally, evaluate the effect of NMES on enrollment and utilization of a formalized exercise program (aim 4).** There will be a separate model for each outcome variable, and the significance of the main and interaction effects will indicate the effect of the intervention over time.

Power Considerations

With at least 27 subjects per group (treatment and sham) completing the study and an alpha level of .05, the ANOVA F test will have approximately 97% power to detect a significant main or interaction effect, assuming a large effect size, and a modest degree of correlation among observations from the same individual. A large effect size in this context is one such that the ratio of the standard deviation of the means to the standard deviation of the observations within the populations is at least 0.4.⁷⁷ In addition, the ANOVA F tests will have at least 69% power to detect main effects and 95% power to detect an interaction effect, with alpha set at .05 and at least a medium effect size (i.e., ratio of standard deviation of means to standard deviation of observations within populations is at least 0.25). Given that we expect a large effect between the groups for many outcomes, in addition to the estimated power of at least 95% for the detection of a Group by Time effect in the presence of a medium to large effect, the sample size chosen for this exploratory study will provide sufficient power to detect this significant group differences over time with a high probability; in addition, this study will allow us to more precisely measure expected power in order to plan future studies.

Section 9: Privacy and Confidentiality Issues

Patients' confidentiality will be preserved by coding each data sheet with a unique subject number, and storing the code number key in a locked file cabinet in a locked research office located in the School of Nursing. Protection against breach of confidentiality is provided by training all individuals involved in the research process about the necessity for complete confidentiality, housing all data collected in locked file cabinets in an access-restricted area, and by use of password protected computers and secure servers. Most data are collected using the REDcap system, and any additional files will be stored in Box Health on IU Servers. Although there can be no absolute guarantee of confidentiality, every practical precaution will be taken.

Section 10: Follow-up and Record Retention

Study recruitment will be ongoing. The duration of the entire study is expected to be 18 months, while each participants expected duration is 6 months. The de-identified data will be retained on computer files indefinitely. Hard copy study documents will be kept in a locked, file cabinet in a locked room. Electronic study information will be stored

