The data collected in this study will be used to prepare a NIH RO1 application, which will launch my independent program of research. Using NMES to improve exercise use in patients with HF is of specific interest to the NIH due to all the potential improvements previously discussed. There is a great potential for extramural funding for development of non-pharmacologic interventions that maintain/improve independence, increase quality of life, decrease hospitalizations, and improve patient outcomes. This study will add to the science by determining if NMES can be used as a stepping stone for enrollment into formalized exercise rehabilitation program, or as an approach for those who are unable to exercise.

Section 3: Inclusion and Exclusion Criteria

Inclusion criteria

Adult patients with a recent hospitalization or clinic visit for heart failure, (ICD-9 428; ICD-10 I50) and one of the following: BNP >400 OR NT-proBNP>900 (If renal dysfunction >1200) OR Echo showing myocardial remodeling, dilation, hypertrophy, or dysfunction will be included in this study. In addition patients must live at home, and not regularly exercise (10 minutes or more a day of exercise most days of the week for the past week).²⁵ Sedentary patients are the focus of this intervention because they would most likely see significant improvement with the intervention.

Exclusion criteria

Patients, who have undertaken cardiac rehab within the 12 months prior to enrollment, have a cognitive or other impairment which prevents accurate application of intervention or inability to provide informed consent, End Stage Renal Disease or receiving mechanical ventilation, receiving non-approved FDA-investigational agents or devices, has received a heart transplant, a destination Ventricular Assist Device (LVAD), pacemaker, or implantable cardiac device, previously used NMES (Neuromuscular electrical stimulation) or TENS (Transcutaneous electrical nerve stimulation) or Uncontrolled arrhythmia's or 3 degree AV heart block, are unable to correctly apply and operate the device even after instruction (as determined by the Research Assistant), those with wounds over area of proper placement of electrodes, or those who are unable to speak and write English. Women who are pregnant or planning to become pregnant.

Children will not be included in this study. Although HF can occur in all ages, it is primarily a disorder of the elderly. In addition the causes of HF in children is very different than adults.

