Section 4: Enrollment and Randomization

Patients who meet eligibility criteria will be referred to the investigator or the research assistant by cardiology, heart failure, or emergency room providers during their routine evaluation of patients eligible for participation in other heart failure research studies through the medical record system. In addition, a clinical research systems

request has been made to allow for notification to the PI the identification all heart failure patients admitted to the hospital so the PI or RA can screen for eligibility. In addition, [name] will release names and contact information for previous participants in her HF study to the PI if the participant has previously indicated they would like to be contacted for future research studies for screening to determine eligibility to participate in this study. The patient will then be contacted by a BISTRO team member for a full explanation of the study and determine interest in participating. If they are interested and are also willing to participate in the FIT Core study (IRB #170755085), an appointment for follow up discussion and possible consenting for both studies) will then be set up for the following week or two. At which time they will come to the school of nursing for final consideration, potential consenting, begin data collection.

In order to ensure that the two groups are comparable between treatment and sham interventions, the participants will be randomized according to gender. Randomization via minimization will be used in order to avoid an unbalanced number of women in the two comparison groups due to chance.²⁶ A file of the computer-generated random assignments will be kept by the research assistant so the PI/data collector remains blinded in a protected Box Health account.

Section 5: Study Procedures

Intervention and Sham/Wait List Control Conditions

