The PI will collect all baseline data before the participant is randomized to the intervention or sham/wait list control group. In order to ensure rigor, patients and PI are blinded to study assignment. The intervention/sham will be set-up by the RA and will be collected after the PI leaves the department so those collecting data will not know which group the participant has been/will be participating in. The RA who is trained in both NMES and Sham intervention will then look at the randomization schedule, and set up and train the participants on equipment use after the data has been collected.²⁷ Once trained, participants will be contacted via phone weekly by the RA who initially trained them (in order to maintain blinding) to determine if participants are following protocol and placement as taught, if the participant is tolerating the intervention, skin condition under the electrodes, and if there are any questions or problems with the machine. The RA applying the intervention will not have any part in the data collection of the rest of the measurements (other than adherence, tolerance and problems with equipment).

The Empi Continuum electrotherapy system made by Empi, Inc. (Clear Lake, South Dakota) is chosen for NMES in this study because it is already available to the PI, it has both the intervention and sham settings, and is able to track adherence (total number of sessions, total session time, average session time, average intensity). Each machine will be calibrated before use for each participant and also checked with each return visit. The output of the stimulator will be checked with an oscilloscope to ensure consistency between the current reading on the stimulator and the actual current output every time the participant returns. NMES will be set up with the machine on simultaneous large muscle atrophy setting with 500 ohm with peak of 50 volts, the “self-adhesive electrodes positioned on the thighs approximately 5 cm below the inguinal fold and 3 cm above the upper patella border” as described by Gobbo.²⁸ When applying the stimulation, the intensity will be gradually increased from an intermittent tingling until a

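### Assignments are not concealed from the research assistant, who may also screen, and device-competence exclusions are judged after assignment with the arm known

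*Combined protocol and SAP*

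**What the plan says.** **Method.** Section 4 says "the participants will be randomized according to gender" and "Randomization via minimization will be used in order to avoid an unbalanced number of women in the two comparison groups due to chance". Gender is the only balancing factor. No allocation probability or other random element is stated.

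**Who holds the assignments.** Section 4: "A file of the computer-generated random assignments will be kept by the research assistant so the PI/data collector remains blinded". The file sits in a protected Box Health account.

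**Who recruits.** Under Section 4, providers refer patients to the investigator or the RA, and hospital admissions are notified to the PI "so the PI or RA can screen for eligibility".

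**Order of events.** Section 5, in its opening part on the two study arms, says: "The PI will collect all baseline data before the participant is randomized to the intervention or sham/wait list control group". Then: "The RA who is trained in both NMES and Sham intervention will then look at the randomization schedule, and set up and train the participants". Both device procedures in Section 12B tell the RA to configure the unit, as TENS or as NMES, before meeting the participant.

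**Exclusion on device competence.** Section 3 excludes patients who "are unable to correctly apply and operate the device even after instruction (as determined by the Research Assistant". Section 6 (Minimizing research-associated risk) says of the teach-back: "If the patient is unable to complete this task, they will be excluded from the study".

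**Analysis set.** Section 8 (Missing Data) relies on maximum likelihood with all available data. It does not define an intention-to-treat set or say how a patient excluded after assignment is handled.

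**The concern.** There are two weaknesses, related but distinct.

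1. **Concealment from the RA.** Blinding the data collector guards against biased measurement. Concealment guards against biased entry, and it has to cover everyone who can influence whether and when a patient is enrolled. Here an unblinded role that may screen also holds the assignments. An RA who knows or can guess the next assignment could, even without intent, encourage, delay or discourage a particular patient.

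2. **Exclusion after assignment.** A competence judgement made by someone who knows the arm, after the arm is fixed, can remove patients differently from the two groups. The procedures differ by arm: the NMES instruction asks for intensity strong enough to contract the muscle, while the sham instruction stops short of contraction. Training may therefore fail at different rates even if the RA is scrupulous. If such patients leave the analysis, the groups compared are no longer those that were randomised.

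The blinded PI protects against neither.

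**Working it through.** The protocol gives no figure on this point to reproduce. The first three steps set the text side by side; the last two size the consequences under stated assumptions.

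**1. Who can know the next assignment.** Section 4 gives the file to the RA, and Section 5 has the RA consult it. Section 4 lets the RA role receive referrals and screen. The stated purpose of the arrangement is to keep the PI/data collector blinded. The protocol describes no independent holder, no release one patient at a time, and no separation of the screening RA from the RA who holds the file.

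**2. Whether the exclusion follows assignment.** Section 6 alone does not place the teach-back before or after allocation. Section 5 does: baseline, then randomisation, then the RA reads the schedule, then training. Section 12B agrees, because the unit is already configured when the RA meets the participant. The exclusion in Section 3 depends on performance after instruction, so as described it is judged with the arm known.

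**3. Whether the analysis repairs it.** Using all available data handles missing visits among patients kept in the study. It does not say that a patient excluded at training is kept.

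**4. Predictability.** If the file lists future assignments, its holder knows 100% of them. If it does not, an RA can still guess from past assignments. Let p be the probability of assigning the under-represented arm within a gender. In the long run, the share of patients who arrive when the arms are level within their gender is

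π₀ = 1 / (1 + 1/(2p − 1)),

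and the share of correct guesses is 0.5·π₀ + p·(1 − π₀).

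| p | π₀ | Correct guesses |
|---|---|---|
| 1 (deterministic) | 1/(1 + 1/1) = 0.500 | 0.250 + 0.500 = 75% |
| 0.8 | 1/(1 + 1/0.6) = 0.375 | 0.1875 + 0.500 = 69% |
| 0.7 | 1/(1 + 1/0.4) = 0.286 | 0.143 + 0.500 = 64% |

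Simulation with 54 patients gives about 75%, 68% and 64%. The values of p are assumptions. For comparison, gender-stratified blocks of varying size (40% women assumed) give about 72% for sizes 2/4, 69% for 4/6 and 67% for 4/6/8.

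**5. Selective exclusion.** Assumptions: no true effect; 27 patients left per arm (the completers in Section 8, Power Considerations); the x least able patients removed from one arm only; correlation 0.5 between ability and outcome; two-sided 5% t test on a standardised outcome.

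| x removed | Bias (SD) | Type I error |
|---|---|---|
| 1 | 0.04 | 5.3% |
| 2 | 0.07 | about 6% |
| 3 | 0.09 | about 6.5% |
| 4 | 0.12 | about 7.6% |

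**The case against.** Much can fairly be said for the plan. The PI is blinded, takes all baseline measures before randomisation, and receives the admission notifications and the names of earlier participants. Several stronger readings also go beyond the text:

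- **That minimisation and a file of assignments contradict each other.** They need not. With gender as the only factor, one sequence per gender can be prepared in advance. The method is loosely labelled and under-specified.
- **That the list is generated in advance.** The words used are a file and a schedule. A file extended after each allocation would also fit.
- **That half of the assignments, 27 of 54, are known with certainty.** This requires minimisation with no random element, which the protocol neither states nor excludes. The 54 also counts planned completers; no number randomised is given.
- **That the same person screens, holds the file and excludes.** The duties belong to the RA role, and the PI may screen instead. More than one RA is possible.
- **That the post-assignment exclusion shows a failure of concealment.** It is a separate problem, of exclusions and the analysis set.

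One could add that the illustrated bias is modest for a study that calls itself exploratory.

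These objections narrow the point without removing it. Nothing described separates the RA's tasks or hides upcoming assignments from an RA who screens, and the sequence in Sections 5 and 12B puts the competence judgement after assignment.

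**Conclusion.** Both weaknesses stand in limited form. Assignments are concealed from the PI but not from the RA, who may screen. The device-competence exclusion is made after assignment with the arm known, and no defined analysis set retains those patients.

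The size depends on facts the protocol leaves open. Foreknowledge is complete if the file lists future assignments. Otherwise it is about 64% to 75% correct guesses, against 50% by chance, for the allocation probabilities examined. One-sided exclusion of 1 to 4 patients would bias a comparison by about 0.04 to 0.12 SD and raise the type I error to about 5.3% to 7.6%, under the assumed correlation of 0.5. These figures show what the procedure permits; they do not show that bias will occur.

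The change should be made, because it is cheap and the study is meant to support a larger grant application. Replacing minimisation is not required: blocks of varying size are about as guessable as minimisation with a random element.

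**What to change.** 1. Have someone with no part in screening or training generate and hold the allocation. Name the algorithm fully: either minimisation on gender with a stated random element, or gender-stratified blocks of varying size.
2. Release assignments through REDCap, already the study's data system, one patient at a time. Release only after consent, eligibility, baseline measures and an arm-neutral check of device application and operation are recorded. Such a check is feasible because both arms share the electrode landmarks, the return demonstration and the patient handout.
3. Have eligibility decided by the blinded PI, or by someone who does not know past assignments. Independent release alone does not stop guessing by an RA who knows past assignments from setting up the devices.
4. State that every randomised patient is analysed in the assigned group, including any who later fail device training. This is needed even with the earlier check, because the intensity instructions differ by arm. It concerns follow-up and analysis only and leaves decisions about device use as they are.

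The cost is protocol wording, one REDCap set-up, and a short device check moved ahead of allocation. If blocks are chosen, gender balance may be slightly looser than under strict minimisation.
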